16.4 Data and Safety Monitoring Board (DSMB)

A DSMB will make recommendations to the Sponsor-Investigator should significant toxicity be observed. The DSMB will meet if 2 of the first 6 subjects have a DLT or at any point after that if more than 30% of subjects have a DLT at the 1.5, 1.2 or 1 mg/m² dose. The DSMB will otherwise meet every 6 months while the study is actively enrolling and has active subjects on trial. If the trial is closed to enrollment and all subjects on study are in follow-up, the DSMB will meet once a year.

16.5 Additional Efficacy Hypotheses

The study is not powered to detect specific hypotheses with regards to correlative endpoints, rather this data and analysis will help better identify subjects having the potential to benefit from this therapy and aid in designing larger Phase III studies.

Summary statistics will be used to for describing changes across time. In addition, the time course of biomarker outcomes will be investigated graphically by summary plots or individual subject plots. Peripheral blood will be analyzed to examine the impact of T cell subpopulations and investigational work using formalin fixed tumor samples for immunohistochemistry and molecular analysis; this work will be exploratory. Categorical data analysis and logistic regression will be used to evaluate the associations between correlative measures and clinical outcome (eg, response, clinical benefit, time to progression, progression-free survival, and survival). If there is suggestion of meaningful trend, methods such as linear mixed models may be used to

characterize the pattern of change over time. Kaplan-Meier methodology and Cox Proportional Hazards models will be used to evaluate time to event endpoints.

16.6 Ethnic and Gender Distribution Chart

Projected Target Accrual

TARGETED / PLANNED ENROLLMENT: Number of Subjects			
Ethnic Category	Sex / Gender		
	Females	Males	Total
Hispanic or Latino	4	4	8
Not Hispanic or Latino	13	13	26
Ethnic Category Total of All Subjects*	17	17	34
Racial Categories			
American Indian / Alaska Native	1	1	2
Asian	3	3	6
Native Hawaiian or Other Pacific Islander	1	1	2
Black or African American	2	2	4
White	8	8	16
More Than One Race	2	2	4
Racial Categories: Total of All Subjects*	17	17	34

17.0 INVESTIGATOR OBLIGATIONS

The Sponsor-Investigator is responsible for the conduct of the clinical trial at the site and is responsible for personally overseeing the evaluation of all study subjects. The Sponsor-Investigator must assure that all study site personnel, including sub-Investigators and other study staff members, adhere to the study protocol and to all applicable regulations and guidelines regarding clinical trials both during and after study completion.

All subjects are informed of the nature of the program, its possible hazards, and their right to withdraw at any time, and each subject signs a form indicating their consent to participate prior to receiving any study-related procedures.

18.0 ADMINISTRATIVE AND REGULATORY CONSIDERATIONS

18.1 Study Site Training

The Sponsor-Investigator is responsible for ensuring that all staff involved in the study are well acquainted with the protocol, study procedures, record keeping and administrative requirements, AE reporting, Good Clinical Practice guidelines, CRF/eCRF completion guidelines, monitoring requirements, and the ability of the site to satisfactorily complete the protocol. Additional documents with instructions for study compliance and CRF/eCRF completion will be provided.

18.2 Documentation

The documentation of clinical data must be stored by the Sponsor-Investigator according to legal requirements. The Sponsor-Investigator and study staff has responsibility for maintaining a comprehensive and centralized filing system containing all study-related documentation. These files must be suitable for inspection by the Sponsor-Investigator, the FDA, and/or other applicable regulatory agencies/competent authorities at any time, and should consist of the following elements: subject files (complete medical records, laboratory data, supporting source documentation, and the Informed Consent); study files (the protocol with all

amendments, copies of all pre-study documentation, and all correspondence between the Competent Authorities, IRB/EC, site, and Sponsor-Investigator); and drug accountability files, containing a complete account of the receipt and disposition of the study drug.

18.3 Data Collection

Electronic case report forms must be completed and submitted for each subject enrolled in the study. Any changes or corrections made to the CRF/eCRF must be subsequently reviewed and signed by the Sponsor-Investigator. All data fields in the CRF/eCRF must be completed to avoid queries.

18.4 Protocol Interpretation and Compliance

The procedures defined in the protocol are carefully reviewed by the Sponsor-Investigator and his/her staff prior to the time of study initiation to ensure accurate representation and implementation. Protocol amendments, if any, are reviewed and implemented promptly following IRB/EC approval. The Sponsor-Investigator is responsible for submitting protocol amendments to the FDA as described in 21 CFR § 312.30 (Protocol Amendments) and other regulatory agencies according to national, state or local requirements. The Sponsor-Investigator, or its designee, is always available to answer protocol- or subject-related questions.

18.5 Study Monitoring and Data Collection

A study monitor may be used to ensure adherence to the protocol, applicable FDA regulations and/or other regulatory agencies national, state or local requirements, and the maintenance of adequate and accurate clinical records. Electronic case report forms are reviewed to ensure that key safety and efficacy data are collected and recorded as specified by the protocol, using the REDcap database platform. The monitor will be permitted to access subject medical records, laboratory data and other source documentation as needed to appropriately monitor the trial. Please reference Section 15 for additional information regarding data management and confidentiality.

18.6 Disclosure of Data/Publication

Individual subject medical information obtained as a result of this study is considered confidential and disclosure to third parties other than those noted below is prohibited. Such medical information may be given to the subject's personal physician or to other appropriate medical personnel responsible for the subject's welfare. Data generated as a result of this study are to be available for inspection on request by the FDA or other regulatory agencies, the Sponsor-Investigator and by the IRB/EC. Public presentation of data in any form will be thoroughly de-identified to ensure confidentiality.

18.7 Ethical Considerations

The Investigator agrees to conduct this study in accordance with applicable United States FDA clinical trial regulations and guidelines, applicable United States FDA clinical trial regulations and guidelines, the ICH (E6) GCP guidelines, the European Union Directive 2001/20/EC for clinical trials conducted in the European Union, the IRB/EC and local legal requirements and with the Declaration of Helsinki (1989). The Investigator will conduct all aspects of this study in accordance with all national, state, and local laws of the applicable regulatory agencies.

18.8 Informed Consent

The Sponsor-Investigator assumes the responsibility of obtaining written Informed Consent from each subject or the subject's legally authorized representative before any study-specific procedures are performed.

Subjects meeting the criteria set forth in the protocol will be offered the opportunity to participate in the study. To avoid introduction of bias, the Investigator must exercise no selectivity with regard to offering eligible subjects the opportunity to participate in the study. Subjects or legal guardians of all candidate subjects will receive a comprehensive explanation of the proposed treatment, including the nature of the therapy, alternative therapies available, any known previously experienced adverse reactions, the investigational status of the study drug, their right to withdraw consent at any time, and other factors that are part of obtaining a proper Informed Consent. Subjects will be given the opportunity to ask questions concerning the study, and adequate time to consider their decision to or not to participate.

Informed Consent will be documented by the use of a written Consent Form that includes all the elements required by FDA regulations and ICH guidelines. The form is to be signed and dated by the subject or subject's legally authorized representative and by the person who administers the consent process. A copy of the signed form will be given to the person who signed it, the

original signed Consent Form will be filed with the subject's medical and/or research records, and copy maintained with the subject's study records. The date of the Informed Consent must be recorded in the source documents.

If an amendment to the protocol changes the subject participation schedule in scope or activity, or increases the potential risk to the subject, the Informed Consent Form must be amended. Any amended Informed Consent must be approved by the IRB/EC prior to use. The revised Informed Consent Form must be used to obtain re-consent from any subjects currently enrolled in the study if the subject is affected by the amendment, and must be used to document consent from any new subjects enrolled after the approval date of the amendment.

18.9 Institutional Review Board/Ethics Committee

The Sponsor-Investigator will assure that an appropriately constituted IRB/EC that complies with the requirements of 21 CFR Section 56 or written assurance of compliance with ICH (E6) guidelines will be responsible for the initial and continuing review and approval of the clinical study. Before initiation of the study, the Sponsor-Investigator or designee will forward copies of the protocol and Consent Form to be used for the study to the IRB/EC for its review and approval.

The Sponsor-Investigator or designee will also assure that all changes in the research activity and all unanticipated problems involving risks to human subjects or others will be reported promptly to the IRB/EC, and that no changes will be made to the protocol without prior IRB approval, except where necessary to eliminate apparent immediate hazards to human subjects.

The Sponsor-Investigator or designee must notify the IRB of SAEs occurring at the site and of safety reports (e.g., IND Safety Reports) received from EMD Serono, in accordance with the IRB's policies.

The Investigator or designee will be responsible for submitting periodic progress reports to the IRB at intervals appropriate to the degree of subject risk involved in the study, but not less than once per year and at the completion or termination of the study.

18.10 Subject Privacy

The Sponsor-Investigator affirms and will uphold the principle of the subject's right to privacy. The Sponsor-Investigator shall comply with applicable national and local privacy laws.

19.0 APPENDICES**19.1 APPENDIX A: ECOG Performance Status Scale****ECOG Performance Status Scale**

GRADE	SCALE
0	Fully active, able to carry out all pre-disease performance without restriction
1	Restricted in physically strenuous activity but ambulatory and able to carry out work of a light or sedentary nature, e.g., light housework, office work
2	Ambulatory and capable of all self-care but unable to carry out work activities. Up and about more than 50% of waking hours.
3	Capable of only limited self-care, confined to bed or chair more than 50% of waking hours.
4	Completely disabled. Cannot carry on any self-care. Totally confined to bed or chair.
5	Dead

19.2 APPENDIX B: Karnofsky Performance Status Scale**KARNOFSKY PERFORMANCE STATUS SCALE**

General	Index	Specific Criteria
Able to carry on normal activity; no special care needed	100	Normal, no complaints, no evidence of disease
	90	Able to carry on normal activity, minor signs or symptoms of disease
	80	Normal activity with effort, some signs or symptoms of disease
Unable to work, able to live at home and care for most personal needs, varying amount of assistance needed	70	Care for self, unable to carry on normal activity or to do work
	60	Requires occasional assistance from others but able to care for most needs
	50	Requires considerable assistance from others and frequent medical care
Unable to care for self, requires institutional or hospital care or equivalent; disease may be rapidly progressing	40	Disabled; requires special care and assistance
	30	Severely disabled, hospitalization indicated, death not imminent
	20	Very sick, hospitalization necessary, active supportive treatment necessary
	10	Moribund
	0	Dead

19.3 APPENDIX C: Study Calendar

Study Flow Chart (for phase I portion)

Please note phase I and phase II schedules differ in that subjects on the phase I portion are required to be evaluated weekly up to week 7. Subjects on the phase II portion of the study and subjects on the phase I portion following week 7 are not required to be evaluated during weeks when they are not receiving therapy.

The study calendar will be managed in Weeks, with each dose of each drug being noted by a Cycle. For example, assuming there are no deviations from the planned schedule events, Week 1 will have Cycle 1 of avelumab and trabectedin. Week 3 will have Cycle 2 of avelumab, Week 4 will have Cycle 2 of trabectedin, Week 5 will have Cycle 3 of avelumab, Week 7 will have Cycle 4 of avelumab and Cycle 3 of trabectedin, etc. This may change based on dose delays or modifications. Weeks should be counted sequentially regardless of what number the dose of each agent is.

Treatment Week	Screening	1	2 ¹³	3	4	5	6 ¹³	7+ ¹⁰	EOT	30D Post EOT	90 Day Post EOT ¹²	LTFU ¹²
Scheduling Window (Days)		± 3	± 3	± 3	± 3	± 3	± 3	± 3	± 3	± 7	± 7	Q12W
Drug Administration ¹	None	A+T	None	A	T	A	None	A+T	None	None	None	
Echo/MUGA ²	X						X ²					
Informed Consent, IC/EC Review, Demographics and Med History	X											
Prior and Con-Med Review	X	X	X	X	X	X	X	X	X	X	X	
Post-study anticancer therapy status										X	X	X
Survival Status									X	X	X	X
Review Adverse Events		X	X	X	X	X	X	X	X	X	X	
Full Physical Examination (to include vitals, weight, ECOG)	X											
Directed Physical Examination (to include vitals, weight, ECOG)		X	X	X	X	X	X	X	X	X		
ECG (Phase 1 only)	X								X	X		
Pregnancy Test – Serum (WCBP Only) ³	X	X		X		X		X ³	X	X		
PT/INR and aPTT	X											
CBC with Differential, Blood Chemistry ⁵	X ⁵	X	X	X	X	X	X	X	X	X		
Urinalysis	X											
CK	X	X			X			X ⁶	X	X		
T3, FT4 and TSH ⁷	X							X ⁷	X	X		
Tumor Imaging ⁸	X							X ⁸	X ⁸			
Archival Tissue Collection (slides) ¹¹	X											
Correlative Studies Blood Collection ⁹		X		X		X		X ⁹	X			

¹A= Avelumab, T = Trabectedin. Avelumab is administered every 2 weeks. Trabectedin is administered every 3 weeks for Cycle 1 and 2 (Week 1 and Week 4), and every 4 weeks after that (Week 7, Week 11, Week 15,...). Trabectedin may be given every 5 weeks if required due to toxicity (see section 9). Please reference Section 7 for additional details.

²ECHO or MUGA to be completed at baseline, week 6, and every 12 weeks while on trabectedin, beginning with week 18.

³Serum pregnancy test to be performed at baseline, and every 2 weeks (or every visit where avelumab is to be administered). Serum pregnancy will also be collected at end of treatment and 30 day follow-up visit. Women of childbearing potential only.

⁵Amylase and Lipase are only to be collected at baseline. Chemistry and LFT panel should include sodium, chloride, potassium, glucose, blood urea nitrogen (BUN), creatinine, calcium, AST, ALT, total bilirubin, alkaline phosphatase, lactic acid dehydrogenase, total protein, and albumin. Reference Table 1 for a full analyte listing.

⁶CK to be performed at all visits where trabectedin is administered. If trabectedin dosing schedule is modified at discretion of investigator to q4weeks or q5weeks or more, the creatine kinase draw should also be modified to follow that schedule.

⁷Thyroid studies should be checked at baseline, week 1, and every 6 weeks (+/- 7 days) (Week 1, Week 7, Week 13...)

⁸Can be done up to 28 days prior to Week 1. While on treatment, tumor imaging should be performed every 12 weeks. Subjects will have their first post-treatment scan during week 12 and every 12 weeks thereafter at the provider's discretion. Imaging schedule will continue every 12 weeks regardless of dose delays or schedule modifications. Tumor imaging will only be performed at EOT visit if not done within 4 weeks of the study visit.

⁹On treatment days, correlative blood should be drawn before study related treatment is administered. Correlative blood will be collected at week 7, and then starting at week 12 every 6 weeks on a treatment day (+/- 7 days). (Week 12, Week 18, Week 24...).

[figure not shown]
¹⁰Additional treatment days where avelumab is administered as a single agent should follow the schedule for Week 3, unless otherwise noted. Additional treatment days where trabectedin is administered and connected/disconnected as a single agent should follow the schedule for Week 4, unless otherwise noted. Additional treatment days where both avelumab and trabectedin are administered should follow the schedule for Week 1, unless otherwise indicated.

¹¹Archival tissue collection does not need to be completed prior to beginning protocol therapy, but every effort should be made to ensure these samples are collected.

¹²The extended safety follow-up beyond 30 days after last avelumab administration may be performed either via a site visit or via a telephone call with subsequent site visit requested in case any concerns noted during the telephone call.

¹³Subjects enrolled to Phase 1 must complete weekly visits through Week 7. Subjects on the Phase II portion of the study and subjects on the Phase I portion after week 7 are not required to be evaluated during weeks when they are not receiving any therapy.

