4.0 TRIAL OVERVIEW

4.1 Study Design

4.1.1 Introduction

This is a Phase I/II, non-randomized, open-label, interventional study of avelumab combined with trabectedin for subjects with advanced L-type sarcoma.

The Phase I stage will evaluate trabectedin (1.5 mg/m²) combined with avelumab (800 mg flat dose). Dose reduction for the trabectedin therapy is permitted after the first cycle. Events which would require a dose reduction of trabectedin are outlined in Section 10, however additional dose reductions may be made at the discretion of the treating clinician down to a lowest possible dose of 1 mg/m². There will be no dose escalation or re-escalation of trabectedin.

4.1.2 Definition of dose limiting toxicity (DLT):

During the phase I portion of the protocol, a DLT will be defined as any grade 3 or higher adverse events, at least possibly-related to protocol therapy, which occur during the first 6 weeks of treatment, with the following specifications and limitations:

- Lab abnormalities that have no clinical sequelae (e.g. febrile neutropenia from low ANC, bleeding from thrombocytopenias etc.) and resolve to grade 1 or better within 7 days will not be considered a DLT.
- Any elevation in total bilirubin > 2x institutional ULN will be considered a DLT.
- Any elevation in AST and ALT over 8x institutional ULN will be considered a DLT.
- ANC <500/ μ L lasting 5 days or more will be considered a DLT.
- Platelets < 25,000/ μ L (grade 4 toxicity) lasting 5 days or more will be considered a DLT.
- Hemoglobin < 7.0 lasting 5 days or more will be considered a DLT.

Additionally, should any grade 5 toxicity (death) occur that is at least possibly-related to treatment (e.g. not easily otherwise explained; for example: a car accident), this will be considered a DLT. In the event of any grade 5 toxicity, enrollment will immediately be put on hold and a data safety monitoring board (DSMB) meeting will be requested immediately.

All clinically significant grade 3 or higher toxicities will be recorded and presented to the DSMB at scheduled meetings. Expected toxicities are those outlined in [Section 10](#). The DSMB will be specifically instructed to consider whether there are increased frequency of known toxicities and to make recommendations accordingly if appropriate. Section 10 summarizes criteria for required dose adjustments.

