Enrollment during the first cohort of the Phase 1 portion of the trial will be staggered. The first subject must have received their second dose of both avelumab and trabectedin prior to treatment of the second subject, and the second subject must have received their second dose of both avelumab and trabectedin prior to treating the third subject. In cases where the first subject's second doses of avelumab and/or trabectedin is delayed beyond week 4, either due to trabectedin toxicity or DLT, or is withdrawn or discontinued from the study, the second subject will be allowed to enroll and start therapy. However, the second subject must complete their second dose of trabectedin and avelumab prior to the start of the third subject.

Should 2 or more DLTs be observed in the first 6 subjects, the starting trabectedin dose will be reduced to 1 mg/m² and the Phase 1 will expand to enroll an additional 6 subjects at the new starting dose. Should two or more DLTs be observed in the 6 subjects enrolled at 1 mg/m² the study will go on hold and a DSMB will meet to discuss if there are modifications that could allow the protocol to safely be re-opened. If <2 DLTs are observed in the 6 subjects on the 1.0 mg/m² cohort, enrollment will expand to a third cohort, enrolling an additional 6 subjects at 1.2 mg/m² of trabectedin. If 2 or more DLTs are observed at 1.2 mg/m², then 1.0mg/m² will be determined to be the recommended Phase 2 dose (RP2D). The highest dose with <2 DLTs will be selected for Phase 2 dosing. If one of the first six subjects does not complete the DLT period for a reason unrelated to toxicity (for example withdrawal of consent or tumor progression) that subject may be replaced.

In Phase 2, the study will go on hold and a DSMB meeting will be triggered if more than 30% of subjects have unexpected, probably related SAE's grade 3 or higher that do not resolve to grade 2 within 2 weeks.

In any subsequent Phase 1 cohorts (1.0 mg/m² dosing and 1.2 mg/m² dosing of trabectedin) subjects may be treated concurrently without delay. Prior to beginning Phase 2, each subject on the phase 1 portion must have received their second dose of both avelumab and trabectedin or completed their treatment (e.g. come off study for symptomatic progression).

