4.1.3 Dosing Administration and Schedule

A treatment schedule is provided in Appendix C. Avelumab will be administered via IV infusion over 60 minutes (+/- 10 minutes). Trabectedin is given as an outpatient 24-hour infusion by pump. During week 1, subjects will receive both drugs: avelumab followed by the standard 24-hour infusion of trabectedin. Following avelumab infusions, subjects must be observed for 60 minutes ± 10 minutes (Cycle 1) or 30 minutes ± 5 minutes (Cycle 2+) post-infusion, prior to beginning trabectedin, for potential infusion-related reactions.

Avelumab will be administered every 2 weeks. Trabectedin will be administered every 3 weeks for the first two doses (Week 1 and Week 4), and then every four weeks (Week 7, Week 11,...) moving forward. After Cycle 2 of trabectedin, dosing may extend to every 5 weeks at investigator discretion, for management of trabectedin-associated toxicity only. Delays of trabectedin beyond 5 weeks may be allowed but require written approval from the Sponsor-Investigator.

It should be noted that trabectedin has significant single agent toxicity. Treatment schedule and evaluation of toxicity are discussed in **Section 7.0**.

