7.2 Administration of agents

Drug	Dose/ Potency	Dose Frequency	Route of Administration	Regimen/ Treatment Period	Use
Avelumab	800 mg flat dose	Q2 Weeks	60 minute (+/- 10 min) IV infusion	Every 2 weeks, regardless of trabectedin dosing	Experimental
Trabectedin	1.5 mg/m ² , 1.2 mg/m ² , or 1.0 mg/m ²	Q3 Weeks (Cycle 1 and 2) Q4 Weeks (Cycle 3+)	24 hour IV infusion	Day 1 of each cycle*	Standard

*Cycles may be adjusted to q5 weeks, or greater with Sponsor-Investigator approval. No schedule adjustments are permitted until after Cycle 2 of trabectedin is administered.

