7.4 Schedule of Treatment Visits

Avelumab will be administered every two weeks starting at Week 1. Dosing may be delayed in response to certain toxicities, as described under Section 10.

Trabectedin will be given every three weeks for Cycle 1 (Week 1) and Cycle 2 (Week 4), and then will be given every 4 weeks (Week 7, Week 11,...). For toxicity management after Cycle 2 (Week 4) Day 1, trabectedin administration may delay to Q5W, as clinically indicated for toxicity management. Delays of trabectedin beyond 5 weeks may be allowed but require written approval from the Sponsor-Investigator.

Administration of either study drug may vary ± 3 days from planned date.

The administration of study drugs during the first 12 weeks (first response assessment timepoint), assuming no dose delays or modifications due to toxicity, is shown below.

The study calendar will be managed in Weeks, with each dose of each drug being noted by a Cycle. For example, assuming there are no deviations from the planned schedule events, Week 1 will have Cycle 1 of avelumab and trabectedin. Week 3 will have Cycle 2 of avelumab, Week 4 will have Cycle 2 of trabectedin, Week 5 will have Cycle 3 of avelumab, Week 7 will have Cycle 4 of avelumab and Cycle 3 of trabectedin, etc. This may change based on dose delays or modifications. Weeks should be counted sequentially regardless of what number the dose of each agent is.

	Week											
Drug	1	2	3	4	5	6	7	8	9	10	11	12*
Avelumab	•		•		•		•		•		•	
Trabectedin	•			•			•				•	

*Response assessment.

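### The six-week DLT window in Section 4.1.2 is not tied to the second trabectedin dose, and no rule makes the cohort decision or the opening of Phase 2 wait for observation after a late one

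*Combined protocol and SAP*

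**What the plan says.** **Window.** Section 4.1.2 defines a DLT as an at least possibly related event of grade 3 or higher, with listed exceptions, limited to events "which occur during the first 6 weeks of treatment".

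**Schedule.** Section 4.1.3: "Trabectedin will be administered every 3 weeks for the first two doses (Week 1 and Week 4". Section 7.4 adds: "Administration of either study drug may vary ± 3 days from planned date". Sections 7.4 and 8.2 and Appendix C number the weeks through any delay: "Weeks should be counted sequentially regardless of what number the dose of each agent is".

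**Delay of the second dose.** The staggering rule in Section 4.1.2 covers a first subject whose second dose "is delayed beyond week 4, either due to trabectedin toxicity or DLT", and sets no upper limit. The footnote to the table in Section 7.2 says: "No schedule adjustments are permitted until after Cycle 2 of trabectedin is administered".

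**Who counts.** Replacement in Section 4.1.2 is optional and covers a subject who "does not complete the DLT period for a reason unrelated to toxicity". No minimum number of doses, and no follow-up after the second dose, is required for a subject to be DLT-evaluable.

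**Decision.** Section 4.1.2: "The highest dose with <2 DLTs will be selected for Phase 2 dosing". Before Phase 2 opens, each Phase 1 subject must have had the second dose of both drugs or have completed treatment. Nothing is said about follow-up after that dose.

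**Section 16.2.** Here a DLT is an unexpected, probably related toxicity of grade 3 or higher. It counts at any time in Phase 1, and a DSMB meeting is called if 30% of subjects have one at any point in the trial.

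**The concern.** The planned window covers two doses with equal follow-up after each. If the second dose slips, the window stays where it is and the time observed after that dose shrinks. A subject delayed for a toxicity that was not itself a DLT, and then followed to the end of week 6, has completed the DLT period. That subject is not replaceable and enters the count of six as DLT-free.

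That count selects the Phase 2 dose. Lost observation time can only lower the number of DLTs seen, so the error runs one way, toward passing a dose. Mandatory weekly Phase 1 visits also end at Week 7 (Appendix C), so close surveillance thins out just when a late second dose would need it.

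**Working it through.** The documents state no operating characteristics for the DLT rule, so there is no plan figure to reproduce.

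**Step 1. Days observed after the second dose.** Inputs: first dose on day 1; planned second dose at Week 4, day 22 (Section 4.1.3); window ends on day 42 (six weeks, Section 4.1.2). Days left, dose day included, are 42 − (22 + delay) + 1 = 21 − delay, with a floor of zero.

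| Delay of second dose | Given on day | Days left of 21 |
|---|---|---|
| none | 22 | 21 |
| 3 days (edge of the visit window) | 25 | 18 |
| 1 week | 29 | 14 |
| 2 weeks | 36 | 7 |
| 3 weeks | 43 | 0 |

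**Step 2. Effect on the decision rule.** Assumptions, none of them from the documents: two-dose DLT risk p of 35% or 30%; the same independent risk r after each dose, spread evenly over 21 days; delayed subjects no more prone to DLTs than others.

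- Per-dose risk: r = 1 − √(1 − p), which is 0.194 at 35% and 0.163 at 30%.
- Risk seen in a delayed subject: d = 1 − (1 − r)^(1 + f), with f = 14/21, 7/21 or 0 for one, two, or three or more weeks late. At 35%, d = 0.302, 0.250 or 0.194. At 30%, d = 0.257, 0.212 or 0.163.
- Chance of passing: P(0 DLTs) + P(1 DLT) among six subjects with these individual risks.

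No delays, 35%: 0.65⁶ + 6 × 0.35 × 0.65⁵ = 0.0754 + 0.2437 = 0.319.

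One subject three or more weeks late, 35%: P(0) = 0.65⁵ × 0.8062 = 0.0935. P(1) = 0.0935 × (0.1938/0.8062 + 5 × 0.35/0.65) = 0.2743. The sum is 0.368.

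| Late subjects | Delay | Pass chance, p = 35% | Pass chance, p = 30% |
|---|---|---|---|
| 0 | – | 0.319 | 0.420 |
| 1 | 1 week | 0.334 | 0.436 |
| 1 | 2 weeks | 0.350 | 0.452 |
| 1 | 3+ weeks | 0.368 | 0.469 |
| 2 | 2 weeks | 0.384 | 0.485 |
| 2 | 3+ weeks | 0.422 | 0.522 |

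One delayed subject therefore moves the pass chance by about 1.5 to 5 percentage points. Two subjects at least two weeks late move it by about 6.5 to 10 points.

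**Step 3. Does another rule close the gap?** The replacement rule does not: it concerns subjects who fail to complete the period for reasons other than toxicity. The condition for opening Phase 2 does not: receipt of the dose is enough, so Phase 2 could open the day after a late dose. Section 16.2 has no six-week limit, but it does not make the cohort decision wait for anyone. Its definition also requires an event to be unexpected, and Section 10.3 lists leukopenia, transaminase, CK and bilirubin elevation, and renal toxicity as expected with trabectedin. The 30% rule triggers a DSMB review; it does not redo the dose selection.

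**The case against.** **Section 16.2 counts late events.** It does, so a reader should not infer that the plan plainly treats such a subject as DLT-free. That is the 4.1.2 reading only. What remains is two sections in conflict and, under either, a decision that can be taken before the late dose has been observed.

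**Delays before the second dose are barred.** The Section 7.2 footnote permits no schedule adjustment until Cycle 2 has been given, yet Section 4.1.2 provides for a second dose delayed beyond week 4. The two passages must be reconciled. While both stand, the delayed case needs a counting rule.

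**A toxicity that holds a dose for weeks would already be a DLT.** Often so: a possibly related grade 3 or higher laboratory abnormality is exempt only if it has no clinical sequelae and resolves within seven days. It is tempting to infer that the delayed subjects are the ones who tolerate the dose worst and all escape the count; the documents do not support that. The gap mainly concerns lower-grade events and delays not caused by toxicity. It is not empty, because Section 4.1.2 names trabectedin toxicity and DLT as separate reasons for delay.

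**The second dose may be reduced.** Section 4.1.1 allows reduction after the first cycle and Section 10.4 requires it for listed toxicities. An event after a reduced dose does not cleanly measure the starting dose. The calculation ignores this, and the point stands against it.

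**A short delay matters little.** Agreed: one week late leaves 14 of 21 days.

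**Conclusion.** The concern holds in a limited form. Section 4.1.2 ends the DLT window by calendar and foresees a late second dose, and no rule ties the fewer-than-two-of-six decision, or the opening of Phase 2, to observation after that dose. On that reading a subject two weeks late contributes one third of the intended follow-up after dose 2, and one three or more weeks late contributes none.

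The effect on the pass chance is modest with one delayed subject (0.32 to 0.33–0.37 at 35% risk; 0.42 to 0.44–0.47 at 30%). It is larger with two subjects two or more weeks late (0.38–0.42 and 0.49–0.52). These sizes rest on assumed DLT risks, equal risk per dose, equal risk in delayed subjects and no dose reduction. The documents do not give the frequency of delays, so the expected effect cannot be stated. The direction, an undercount of DLTs, does not depend on the assumed risk.

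A reader might blame the sequential week counting in Appendix C. That sentence only labels weeks. Six weeks of treatment is a fixed period with or without it; the defect lies in Sections 4.1.2 and 16.2.

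**What to change.** 1. Reconcile Sections 4.1.2, 7.2 and 16.2 so that there is one DLT definition, one window, and one statement on whether the second trabectedin dose can be delayed.
2. State in Sections 4.1.2 and 16.2 that a subject counts as DLT-free for the six-subject rule only after the 21 days of observation following the second trabectedin dose that the planned schedule already gives.
3. Say how subjects whose second dose was reduced, or never given, are counted.
4. Make the cohort decision and the opening of Phase 2 wait until all six windows have closed, or until the DLT count has already settled the decision.

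No change to Appendix C is needed. The cost is protocol wording, plus a cohort decision that waits by the length of the delay when a second dose is late.
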